10.2 T Cell Studies

We will test the hypothesis that milk-specific T cells will be primarily CD4+, IL-5+, IL-13+, consistent with prior work.⁴⁷⁻⁴⁹ Furthermore, we will test the sub-hypothesis that the level of milk-specific T cells will positively correlate with positive atopy patch tests to milk and the response rate to milk elimination (1FED and secondarily 6FED, which also contains milk). The frequency of Th2 cells will be determined by FACS analysis, and milk-specificity will be estimated by milk protein stimulation in vitro, particularly looking at CD154 induction, a marker of T cell activation. These exploratory studies, will be performed with shipped blood samples, by [name], as published.^{47,48,50,51} The study will be limited to a pilot analysis of patients who only enter the 1FED and we will compare patients with positive and negative skin tests (prick and patch).

10.3 Biospecimen Storage

Blood, saliva, and/or esophageal biopsies may be collected and stored for future analysis. Specimens will be obtained at one of the participants’ study visits and will be used for DNA isolation. Blood will be drawn by a certified phlebotomist or an RN, LPN, DO, or MD. A standard protocol for collection of blood derived DNA will be utilized, and approximately 2 teaspoons (10 mL) of blood will be collected. If blood cannot be obtained or the subject elects to limit DNA collection to non-blood sources, an oral DNA specimen (saliva) will be obtained

instead. Whether the sample collected is blood, tissue, or saliva, samples will be deidentified, processed, and shipped to CCHMC for storage. DNA will remain available for future genetic testing.

11.CRITERIA FOR PARTICIPANT AND STUDY COMPLETION AND PREMATURE STUDY TERMINATION

11.1 Participant Completion

Participant completion is defined by completion of the EGD at the end of Phase 1 and Phase 2 (for those who choose to continue into Phase 2); there are two levels of completion, those that complete Phase 1 and those that complete Phase 2.

11.2 Participant Stopping Rules and Withdrawal Criteria

Participants may be prematurely terminated from the study for the following reasons:

1. The participant elects to withdraw consent from all future study activities, including follow-up.
2. Participant is unable to comply with the dietary restrictions.
3. Participant develops severe complications from their EoE (for instance, esophageal strictures)
4. Participant becomes pregnant.
5. The participant is “lost to follow-up” (i.e., no further follow-up is possible because attempts to reestablish contact with the participant have failed).
6. The participant develops an SAE related to therapy in Phase 1 or 2 of the study.
7. The participant dies.
8. The Investigator no longer believes participation is in the best interest of the participant.

11.3 Participant Replacement

Enrolled participants who start on the initial dietary protocol and prematurely discontinue/withdraw from the study will be replaced if they do not reach Week 6 of the study including the EGD. Additional participants will be enrolled in the same manner as all other participants. Participant numbers will not be re-used. Any enrolled participant will be included into any intent to treat analysis.

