4. STUDY DESIGN

4.1 Description of Study Design

We will be recruiting a total of 136 participants, between the ages of 18-60. Participants will be enrolled in this study based on the presence of active eosinophilic esophagitis and adherence to the inclusion and exclusion criteria.

[figure not shown]
We intend to conduct a prospective non-blinded randomized trial that compares a 1-food elimination diet (1FED) versus a 6-food elimination diet (6FED) for six weeks (Phase 1). Subsequently, non-responders to 1FED dietary elimination therapy will be treated with 6FED and non-responders to 6FED will be treated with SGC (swallowed fluticasone at a dose of 880 mcg twice a day) for six weeks (Phase 2) while on an unrestricted diet, if the participant chooses to continue in to Phase 2. The empiric dietary therapy interventions are as follows: 1-food elimination diet (1FED)—avoidance of milk vs. 6-food elimination diet (6FED)—avoidance of milk, egg, wheat, soy, fish/shellfish, and peanut/tree nuts, for six weeks. Milk elimination for both 1FED and 6FED includes all mammal milk (i.e. goat, sheep, and cow's milk must all be eliminated). The study design is shown schematically in Figure 1 Study Design Flowchart.

In Phase 1, all participants will be randomized 1:1 to either 1 food elimination (milk elimination alone, 1FED) or 6 food elimination (milk, egg, wheat, soy, fish/shellfish, peanut/tree nuts elimination, 6FED) therapeutic diet. At the end of this phase, an EGD will be performed to assess remission. Attainment of remission (esophageal eosinophil counts <15 eosinophils/high powered field) after Phase 1 will result in study discontinuation and maintenance of the “successful” dietary therapy. Treatment non-responders may choose whether or not to continue into Phase 2. Dietary therapy non-responders who were on 6FED in Phase 1 and continue in to Phase 2 will receive topical swallowed steroids for six weeks (Phase 2) followed by EGD with esophageal biopsies. These participants will return to an unrestricted diet (i.e. stop 6FED) prior to beginning topical swallowed steroid therapy. Dietary non-responders in Phase 1 who were on 1FED and continue in to Phase 2 will continue to a 6FED therapeutic diet (Phase 2) for six weeks followed by EGD with esophageal biopsies to assess remission.

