13.6 Sample Size Considerations

The sample size was based on the primary endpoint of the percent of patients in histologic remission (<15 eosinophils/hpf) at the end of Phase 1. Based on preliminary data, it is assumed that the remission rate for the 1FED population is 45%.¹⁶ We assume that the remission rate in the 6FED population will be increased to 70%. A sample size of 60 patients per group (120 total patients) will provide at least 80% power to detect a difference in rates between groups of 25% at the two-sided $\alpha=0.05$. This calculation is based on a likelihood ratio test statistic for comparing proportions. To allow for a potential approximate 15% drop-out, the sample size will be increased to 68 patients per group (136 total patients). This calculation was performed using the PASS vers. 12 software. The following table displays the robustness of the sample size under various response rate and drop-out rate scenarios.

Sample Size per group	Difference to detect with 80% power if 1FED rate is 45%	Difference to detect with 80% power if 1FED rate is 50%	Difference to detect with 80% power if 1FED rate is 55%
56	26%	24%	24%
60	25%	23.5%	23.5%
64	24%	23%	23%
68	24%	23%	22%

14.IDENTIFICATION AND ACCESS TO SOURCE DATA

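### Drop-outs are allowed for, replaced and kept in ITT all at once, so 136 is not a firm number randomised and section 13.6 does not give power for the planned primary analysis

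*Protocol*

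**What the plan says.** Three provisions deal with the same patients.

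- **Allowance.** Protocol 13.6 states that "A sample size of 60 patients per group (120 total patients) will provide at least 80% power". It then allows for about 15% drop-out: "the sample size will be increased to 68 patients per group (136 total patients". The rates behind this are given as "it is assumed that the remission rate for the 1FED population is 45" per cent and "We assume that the remission rate in the 6FED population will be increased to 70" per cent.
- **Replacement.** Protocol 11.3 covers enrolled participants who start the initial diet. Those who "prematurely discontinue/withdraw from the study will be replaced if they do not reach Week 6 of the study including the EGD". Additional participants are enrolled in the usual way.
- **Retention.** The same section adds: "Any enrolled participant will be included into any intent to treat analysis". Protocol 13.4.1 puts all randomised patients in the primary analysis and imputes failure where remission cannot be determined. The SAP (Analysis Populations) imputes failure in the same way, but excludes patients who were randomised inappropriately and never completed the enrolment visit.

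On the total, Protocol 4.1 says "We will be recruiting a total of 136 participants, between the ages of 18-60", and the SAP's study design section repeats 136. Neither document gives a maximum number randomised or a target number of completers. The SAP does not mention replacement.

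**The concern.** Adding patients for drop-out makes sense when drop-outs are removed from the analysis and the remaining patients show the assumed rates. That is not the planned primary analysis. Here drop-outs stay in the denominator, and those without an endpoint count as failures, which pulls both remission rates down and narrows the difference to be detected. Section 13.6 makes no allowance for this.

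The replacement rule then leaves the size of the trial open. Taken literally, the first replacement carries enrolment past 136. A reader cannot tell whether 136 means patients randomised, patients completing, or a ceiling that includes replacements. At stake are the number of patients exposed and budgeted for, the point at which recruitment to an open-label trial ends, and whether the 80% claim applies to the primary test.

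**Working it through.** **Inputs.** Remission 45% on 1FED and 70% on 6FED; two-sided alpha 0.05; likelihood ratio test for two proportions; 60 per group raised to 68; drop-out about 15% (all Protocol 13.6). Allocation 1:1 (4.6). Failure imputation (13.4.1). Equal drop-out in the two arms is my assumption.

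**Formula.** With n per group and p̄ the mean of the two rates,

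power = Φ{ [ |p₂ − p₁|√n − 1.96√(2p̄(1 − p̄)) ] / √( p₁(1 − p₁) + p₂(1 − p₂) ) }.

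Exact enumeration of the likelihood ratio test is given beside it. Both ignore the covariates and the site effect of the planned mixed model, as 13.6 does.

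**1. The plan's own figure.** n = 60, 0.45 vs 0.70: (0.25 × 7.746 − 1.96 × 0.699) / 0.676 = 0.837, so power is 79.9% (exact 80.6%). The base calculation reproduces.

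**2. The allowance.** 60/68 = 0.882, so 68 per group covers 11.8% drop-out. At 15%, 60/0.85 gives 71 per group.

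**3. Number randomised under replacement.** If every drop-out is replaced until 68 per group complete, 68/0.85 = 80 per group, or 160 in total.

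**4. Rates under failure imputation.** If 45% and 70% are completer rates and no drop-out has a usable biopsy, 0.45 × 0.85 = 38.25% and 0.70 × 0.85 = 59.5%. The difference falls from 25 to 21.25 points.

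- n = 68 (136 randomised, no replacement): (0.2125 × 8.246 − 1.96 × 0.707) / 0.691 = 0.531, power 70.2% (exact 69.9%).
- n = 80 (about 160 randomised): (0.2125 × 8.944 − 1.96 × 0.707) / 0.691 = 0.746, power 77.2% (exact 76.8%).
- 80% power would need about 86 per group (172 in total).

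**5. Other drop-out rates, same assumptions (normal approximation).**

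| Drop-out per arm | 136 randomised, no replacement | Replacement to 136 completers |
|---|---|---|
| 5% | 80.1% | 82.4% (144 randomised) |
| 10% | 75.3% | 79.9% (152) |
| 11.8% | 73.5% | 79.2% (156) |
| 15% | 70.2% | 77.2% (160) |
| 20% | 65.1% | 74.9% (170) |

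**6. Some drop-outs biopsied.** If half of a 15% drop-out is biopsied and remits at the assumed rates (assumption), 7.5% are imputed: 0.45 × 0.925 = 41.6% vs 0.70 × 0.925 = 64.75%. Exact power is 77.4% at 68 per group and 83.6% at 80 (normal 77.7% and 84.1%).

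**7. Rates already counting drop-outs as failures.** 45% vs 70% applies unchanged: 84.7% at 68 per group (exact 84.2%) and 90.0% at 80 (exact 89.6%).

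**8. Unequal drop-out (assumption), 68 per group, all imputed as failures.** With 10% on 1FED and 20% on 6FED: 40.5% vs 56%, power about 44%. With 20% and 10%: 36% vs 63%, about 89%.

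**The case against.** The best defence is that 13.6 never says what the 45% and 70% represent. It calls them rates in the two diet populations. If they already count drop-outs as failures, the trial has more than 80% power at 68 per group and nothing is lost. This stands as a possible reading, though the drop-out allowance would then serve no purpose.

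Second, not every replaced patient becomes a failure. Protocol 9.4 applies the end-of-treatment procedures, including biopsies, to early withdrawals, within a week of stopping the diet. Only patients whose remission cannot be determined are imputed. This also stands, so step 4 is an upper bound on the loss for equal 15% drop-out.

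Third, section 11.3 covers only participants who start the diet. Those randomised who never start are not replaced, so the allowance and the replacement rule do not fully duplicate each other, and 136 completers is one reading among several.

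Some stronger readings are tempting and not supported:

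- A reader might infer that replacement costs power. It adds patients and raises power, from about 70% to about 77% in step 4.
- A reader might infer that the 80% figure is miscalculated. It reproduces for the 60 per group to which 13.6 attaches it.
- A reader might take the 44% in step 8 as a forecast. The documents give no drop-out by arm, and the opposite pattern gives about 89%.
- A reader might worry that replacement leaves completers unbalanced between arms. The primary analysis is ITT and does not need balanced completers.

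**Conclusion.** The point holds in two parts of different strength. That 136 is not a firm number randomised follows from the text alone: 11.3 requires replacement, and neither document states a cap. That 13.6 does not give power for the planned primary analysis also follows, because it sizes on rates undiluted by failure imputation and does not say what those rates include.

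The size of any shortfall is conditional. It requires completer rates, equal 15% drop-out and no usable biopsy from any drop-out. Power is then about 70% without replacement and about 77% with full replacement to 136 completers. With replacement, as the protocol is written, the gap is about 3 points at 15% drop-out, about 1 point at the 11.8% that 68 per group covers, and nil at 5%. A claim that the trial is underpowered outright goes further than the documents allow.

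**What to change.** 1. In Protocol 11.3, 4.1 and 13.6 and in the SAP, state whether 136 is a cap on randomisation or a target number of completers, and give the maximum number randomised.
2. Use one drop-out rule. Either remove replacement and treat 136 as the number randomised, or keep replacement, call 136 the completer target and stop describing it as a drop-out allowance.
3. In 13.6, state whether 45% and 70% count drop-outs as failures.
4. Restate the power for the ITT analysis with failure imputation. For completer rates and 15% drop-out this is about 70% at 136 randomised or about 77% at about 160. Neither reaches 80%, which would take about 172 randomised under the same assumptions. State the share of early withdrawals expected to have a biopsy if credit is taken for it. If unequal drop-out is shown, give both directions.

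The cost is wording in four places and a less favourable power statement. Keeping replacement also means declaring a larger maximum enrolment. No treatment, visit or clinical rule changes.

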11.4 Follow-up after Early Study Withdrawal

Refer to section 9.7.

11.5 Study Stopping Rules

The study can be terminated or stopped at the site for reasons including but not limited to:

1. Investigator or sponsor request to withdraw from study participation.
2. Serious and/or persistent noncompliance by the investigator with the protocol or other local applicable regulatory guidelines in conducting the study.
3. IRB decision to terminate or suspend approval for the investigation or the investigator.

12.SAFETY MONITORING AND REPORTING

12.1 Overview

This section defines the types of safety data that will be collected under this protocol and outlines the procedures for appropriately collecting, grading, recording, and reporting those data. Adverse events that are classified as serious according to the definition of the FDA must be reported promptly (per Section 12.5.1, *Reporting of Serious Adverse Events and Adverse Events to DAIT/NIAID*). Appropriate notifications will also be made to site principal investigators and the Institutional Review Board (IRB).

Information in this section complies with *ICH Guideline E2A: Clinical Safety Data Management: Definitions and Standards for Expedited Reporting*, *ICH Guideline E-6: Guideline for Good Clinical Practice*, 21CFR Parts 312 and 320, and applies the standards set forth in the National Cancer Institute (NCI), Common Terminology Criteria for Adverse Events (CTCAE), Version [enter 4.0 or correct version applicable to trial] : <http://ctep.cancer.gov/reporting/ctc.html>.

Safety will be assessed through documentation of AEs, adverse drug reactions, physical examination findings and vital signs, and pre- and post-treatment morning cortisol for those patients on SGC in Phase 2.

12.2 Definitions

12.2.1 Adverse Event (AE)

An Adverse Event is any untoward or unfavorable medical occurrence associated with the subject's participation in the research, whether or not considered related to the subject's participation in the research (modified from the definition of adverse events in the 1996 International Conference on Harmonization E-6 Guidelines for Good Clinical Practice) (from OHRP "Guidance on Reviewing and Reporting Unanticipated Problems Involving Risks to Subjects or Others and Adverse Events (1/15/07)" <http://www.hhs.gov/ohrp/policy/advevntguid.html#Q2>.)

For this study, an adverse event will include any untoward or unfavorable medical occurrence associated with:

Study therapy regimen: Topical swallowed steroids

- Development of oral thrush
- Behavior change
- Difficulty sleeping
- Bone demineralization
- Elevated blood sugar
- Hypertension
- Eye changes such as glaucoma or cataracts
- Potential for adrenal suppression
- Potential risk of immunosuppression

12.2.2. Study mandated procedures:

Esophagogastroduodenoscopy (EGD) Biopsies

- Bleeding at the site of biopsy collection
- Perforation of the stomach, duodenum or esophagus

Allergen Scratch Skin Testing

- Prolonged (>24 hours) itching at test site
- Swelling (> 10 cm) at site of test lasting more than 24 hours
- Nasal allergic symptoms within 30 minutes of the procedure
- Fainting/Vasovagal event within 30 minutes of the procedure
- Anaphylaxis

Blood Draws

- Fainting/Vasovagal events
- Bruising at puncture site larger than 2 cm diameter
- Bleeding from puncture site lasting more than 30 minutes
- Swelling at puncture site larger than 2 cm

12.2.3 Suspected Adverse Reaction (SAR)

Suspected adverse reaction (SAR) means any adverse event for which there is a reasonable possibility that the investigational study therapy regimen caused the adverse event. For the purposes of safety reporting, ‘reasonable possibility’ means there is evidence to suggest a causal relationship between the drug and the adverse event. A suspected adverse reaction implies a lesser degree of certainty about causality than adverse reaction, which means any adverse event caused by a drug (21 CFR 312.32(a)).

12.2.4 Unexpected Adverse Event

An adverse event or suspected adverse reaction is considered “unexpected” if it is not listed in the GlaxoSmithKline *package insert* or is not listed at the specificity, severity or rate of occurrence that has been observed; or is not consistent with the risk information described in the protocol.

“Unexpected” also refers to adverse events or suspected adverse reactions that are mentioned in the package insert as occurring with a class of drugs or as anticipated from the pharmacological properties of the drug, but are not specifically mentioned as occurring with the particular drug under investigation (21 CFR 312.32(a)).

12.2.5 Serious Adverse Event (SAE)

An adverse event or suspected adverse reaction is considered “serious” if, in the view of either the investigator or DAIT/NIAID, it results in any of the following outcomes (21 CFR 312.32(a)).

Death: A death that occurs during the study or that comes to the attention of the investigator during the protocol-defined follow-up period must be reported whether it is considered treatment related or not.

A life-threatening event: An AE or SAR is considered “life-threatening” if, in the view of either the investigator or DAIT/NIAID, its occurrence places the subject at immediate risk of death. It does not include an AE or SAR that, had it occurred in a more severe form, might have caused death.

Inpatient hospitalization or prolongation of existing hospitalization.

Persistent or significant incapacity or substantial disruption of the ability to conduct normal life functions.

Congenital anomaly or birth defect.

Important medical events that may not result in death, be life threatening, or require hospitalization may be considered serious when, based upon appropriate medical judgment, they may jeopardize the subject and may require medical or surgical intervention to prevent one of the outcomes listed above.

Elective hospitalizations or hospital admissions for the purpose of conduct of protocol mandated procedures are not to be reported as an SAE unless hospitalization is prolonged due to complications.

12.3 Grading and Attribution of Adverse Events

12.3.1 Grading Criteria

The study site will grade the severity of adverse events experienced by the study subjects according to the criteria set forth in the National Cancer Institute’s Common Terminology Criteria for Adverse Events (CTCAE) [*Version 4.03, June 14, 2010*] This document (referred to herein as the NCI-CTCAE manual) provides a common language to describe levels of severity, to analyze and interpret data, and to articulate the clinical significance of all adverse events. The NCI-CTCAE has been reviewed by the Protocol Chair and has been deemed appropriate for the subject population to be studied in this protocol.

Adverse events will be graded on a scale from 1 to 5 according to the following standards in the NCI-CTCAE manual:

Grade 1 = mild adverse event.

Grade 2 = moderate adverse event.

Grade 3 = severe and undesirable adverse event.

Grade 4 = life-threatening or disabling adverse event.

Grade 5 = death.

For grading an abnormal value or result of a clinical or laboratory evaluation (including, but not limited to, a radiograph, an ultrasound, an electrocardiogram etc.), a treatment-emergent adverse event is defined as an increase in grade from baseline or from the last post-baseline value that doesn’t meet grading criteria. Changes in grade from screening to baseline will also be recorded as adverse events, but are not treatment-emergent. If a specific event or result from a given clinical or laboratory evaluation is not included in the NCI-CTCAE manual, then an abnormal result would be considered an adverse event if changes in therapy or monitoring are implemented as a result of the event/result.

12.3.2 Attribution Definitions

The relationship, or attribution, of an adverse event to the study therapy regimen or study procedure(s) will initially be determined by the site investigator and recorded on the appropriate AE case report form. Final determination of attribution for safety reporting will be determined by DAIT/NIAID. The relationship of an adverse event to study therapy regimen or procedures will be determined using the descriptors and definitions provided in Table 12.3.2.

For additional information and a printable version of the NCI-CTCAE manual, consult the NCI-CTCAE web site: <http://ctep.cancer.gov/reporting/ctc.html>.

Table 12.3.2 Attribution of Adverse Events

Code	Descriptor	Relationship (to primary investigational product and/or other concurrent mandated study therapy or study procedure)
UNRELATED CATEGORY		
1	Unrelated	The adverse event is clearly not related: there is insufficient evidence to suggest a causal relationship.
RELATED CATEGORIES		
2	Possible	The adverse event has a reasonable possibility to be related; there is evidence to suggest a causal relationship.
3	Definite	The adverse event is clearly related.

